Secondary objectives: *Key secondary objectives:*

- To demonstrate the effect of pegcetacoplan on the number of packed red blood cell (PRBC) transfusions in patients with CAD.
- To demonstrate the effect of pegcetacoplan on health-related quality of life in patients with CAD.

Other secondary objectives:

- To assess the effect of pegcetacoplan on clinical laboratory markers of hemolysis and transfusion dependence in patients with CAD.
- To determine the durability of response in patients with CAD receiving pegcetacoplan.
- To assess tolerability, safety and immunogenicity of pegcetacoplan in patients with CAD.
- To describe long-term effect of pegcetacoplan in patients with CAD.
- To evaluate the pharmacokinetics (PK) of pegcetacoplan following twice-weekly s.c. infusions.
- To evaluate the effect of pegcetacoplan in complement biomarkers.

STUDY ENDPOINTS

Primary endpoint: Response to treatment at Week 24.

Response is defined as:

- An increase in hemoglobin (Hb) of ≥ 1.5 g/dL from Baseline or Hb normalization at Week 16; AND
- Maintenance of this effect from Week 16 to Week 24; AND
- The absence of PRBC transfusions (between Week 5 and Week 24).

Note: Hb normalization is defined as within normal range (between the defined upper and lower limits of normal [ULN and LLN]), as set by the testing laboratory.

Key secondary endpoints:

- Change from Baseline to Week 24 in Hb level.
- Transfusion avoidance (Yes/No) from Week 5 to Week 24.
- Change from Baseline to Week 24 in the Functional Assessment of Cancer Therapy—Anemia/Fatigue (FACT-An) score.

Secondary efficacy endpoints:

Part A:

- Number of PRBC transfusions from Week 5 to Week 24.
- Change from Baseline to Week 24 in the following:
 - Lactate dehydrogenase (LDH) level.
 - Haptoglobin level.
 - Indirect bilirubin level.
 - Absolute reticulocyte counts (ARC).
 - D-dimer level.
- Normalization of markers of hemolysis at Week 24, specifically:
 - LDH level.
 - Indirect bilirubin level.
 - ARC.
- Time to first normalization from Baseline to Week 24 for the following:
 - Hb level.
 - LDH level.
 - Indirect bilirubin level.
 - ARC.
- Number of PRBC units transfused from Week 5 to Week 24.
- Change from Baseline to Week 24 in the following:
 - Functional Assessment of Chronic Illness Therapy-Fatigue (FACT-F) subscale score of the FACT-An scale.
 - 12-Item Short Form Survey (SF-12) score.
 - 5-Level EuroQol 5-Dimension (EQ-5D-5L) score.

Part B:

- Change from Baseline to Week 48 in the following:

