Patients will be randomized in a ratio of 2:1 to receive either pegcetacoplan or placebo, respectively. The randomization will be stratified by transfusion history (number of transfusions during the 6-month period prior to randomization \geq 1; 0). Every effort should be made to enroll patients in both subgroups.

The planned length of participation in the study for each patient is a maximum of 110 weeks. This study will consist of 5 periods:

- Screening period: up to 4 weeks (may be extended by up to 2 additional weeks).
- Double-blind treatment period: 24 weeks (Part A).
- Open-label treatment period: 24 weeks (Part B).
- Open-label maintenance period: up to additional 48 weeks or until the product becomes commercially available (Part C).
- Follow-up period: 8 weeks.

Screening period (up to 4 weeks; may be extended by up to 2 additional weeks)

Informed consent will be obtained during a screening visit prior to any study-related procedures being conducted. Patients experiencing acute hemolytic crisis may receive blood cell transfusions during the screening period. The start of dosing must occur at least 7 days after receiving last transfusion.

Patients will be screened to confirm that the patient selection criteria for the study have been met. Key inclusion and exclusion criteria will be reviewed by the study medical monitor and eligibility will be confirmed prior to the enrollment. If needed and after consultation with the medical monitor, the screening period may be extended by up to 2 additional weeks (e.g., eligibility laboratory results not available due to technical reasons or the patient receives an RBC transfusion during the last week of the screening period, reasonably reversible medical reasons such as COVID-19 infection).

Double-blind treatment period (24 weeks): Part A

A total of 57 patients who meet all of the inclusion criteria and none of the exclusion criteria will be randomized in a 2:1 ratio to either pegcetacoplan or placebo. Safety and efficacy will be assessed.

Patients randomized into the study will receive s.c. IMP (pegcetacoplan or placebo) twice weekly for 24 weeks.

All standard-of-care medications can be continued, with the exception of protocol-defined prohibited medications.

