6.5 Efficacy, safety, pharmacokinetic, pharmacodynamic and other assessments

6.5.1 Medical history

Medical history will be recorded at screening. Investigators should document the occurrence, signs, and symptoms of the patient's preexisting conditions, including all prior significant illnesses, up to and including 1 year before screening. Information on CAD history will be collected including all prior lines of therapy. Additional preexisting conditions, present at the time when informed consent is given, up to the time of first dosing, are to be regarded as concomitant. The number of transfusions received during the 6-month period prior to randomization in this study will be recorded. Medical history will also include alcohol consumption and smoking history, if applicable.

Illnesses first occurring or detected during the study and worsening of a concomitant illness during the study are to be documented as AEs on the eCRF in accordance with Section 6.5.4.1.2.

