8.3.4.2 Analysis of secondary efficacy endpoints: Part A

All secondary efficacy analyses will be analyzed with the ITT set.

The number of PRBC transfusions from Week 5 to Week 24 in each treatment group will be compared using a negative binomial regression model. The model-based estimate of the treatment effect and corresponding 95 % CI and p-value will be calculated. Patients who withdraw from treatment or receive prohibited medication before Week 24 will have the number of transfusions estimated from the duration that they were in the study until withdrawal or initiation of prohibited medication.

The change from Baseline at Week 24 in LDH, haptoglobin, indirect bilirubin, ARC and D-dimer will be analyzed using MMRM analysis with the fixed effects of treatment, strata, visit, visit-by-treatment interaction, and the respective Baseline level as covariate, using an unstructured covariance matrix and the Kenward-Roger method for calculating the degrees of freedom. Should the model fail to converge with an unstructured covariance matrix, other covariance structures will be explored. Details will be described in the SAP. The difference between treatment groups will be estimated, along with its 95 % CI and p-value. All data after the ICEs (as described in Section 8.3.4.1) will be set to missing, and the strategy for handling ICEs will be the same as that for the analysis of change from Baseline to Week 24 in Hb, as described in Section 8.3.4.1.

For the endpoint regarding the normalization of markers of hemolysis (LDH, indirect bilirubin and ARC), at Week 24, the number and percentage of patients who respond will be tabulated by treatment group and compared between treatment groups using an exact CMH test stratified for the strata ($\geq 1 / 0$ transfusions during the 6-month period prior to randomization). The strategy for handling ICEs will be the same as for the primary endpoint where patients meeting an ICE will be considered not normalized.

Kaplan-Meier plots will be presented for the time-to-event endpoints of time to normalization from Baseline to Week 24 for LDH, Hb, indirect bilirubin and ARC for each treatment group at Week 24, and survival estimates will be provided.

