The number of units of PRBCs transfused from Week 5 to Week 24 in each treatment group will be compared using a Wilcoxon rank-sum test. The difference between the medians will be estimated along with its 95 % CI. Patients who withdraw from treatment or study or receive prohibited medication before Week 24 will have the number of units estimated from the duration that they were in the study until withdrawal or initiation of prohibited medication.

The change from Baseline at Week 24 in FACIT-F, SF-12 and EQ-5D-5L will be analyzed using MMRM with the fixed effects of treatment, strata, visit, visit-by-treatment interaction and the respective Baseline level as covariate, using an unstructured covariance matrix and the Kenward-Roger method for calculating the degrees of freedom. Should the model fail to converge with an unstructured covariance matrix other covariance structures will be explored. Details will be described in the SAP. The difference between treatment groups will be estimated, along with its 95 % CI and p-value. All data after the ICEs (as described in Section 8.3.4.1) will be set to missing, and the strategy for handling ICEs will be the same as that for the analysis of change from Baseline to Week 24 in Hb, as described in Section 8.3.4.1.

Summary statistics by treatment groups will be presented at each assessment visit during the 24-week double-blind treatment period.

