#### **7.3.1 Number of PRBC transfusions from Week 5 to Week 24.**

The number of PRBC transfusions from Week 5 to Week 24 in each treatment group will be compared using a stratified Wilcoxon rank-sum test-p-value will be calculated. Crude rates of transfusions will be calculated for the double-blind period (Part A). Patients who withdraw from randomized treatment or receive prohibited medication before Week 24 will have the number of transfusions estimated from the duration that they were in the study until withdrawal or initiation of prohibited medication.

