### **7.3.4 Number of units of PRBCs transfused from Week 5 to Week 24**

The number of units of PRBCs transfused from Week 5 to Week 24 in each treatment group will be compared using a stratified Wilcoxon rank-sum test (i.e., the Van Elteren test). Patients who withdraw before Week 24 will have the number of units estimated from the duration that they were in the study until withdrawal or initiation of prohibited medication.

The average number of units transfused for the duration where a patient has evaluable data for PRBC transfusions will be used to estimate the total number of transfused units that would have been used through Week 24 had they not withdrawn from the study.

If the number of PRBC is reported in units and mL in the database the mL will be converted to units using the following formula:

$$\text{Number of PRBC units} = \text{Round}(\text{PRBC (mL)} / 300), 1.$$

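### The test of number of PRBC transfusions (SAP 7.3.1) uses prior transfusion history only as ≥ 1 versus 0, although each patient's 6-month count is recorded

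*Protocol*

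**What the plan says.** **What is collected.** Protocol 6.5.1 states: "The number of transfusions received during the 6-month period prior to randomization in this study will be recorded". SAP 6.3.1 lists prior transfusions in those 6 months for descriptive summary. Randomization uses only ≥ 1 versus 0. The Protocol synopsis puts it as "The randomization will be stratified by transfusion history (number of transfusions during the 6-month period prior to randomization", followed by those two levels, and Protocol 6.4.3 and SAP 2.4 agree.

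**How the two transfusion-burden endpoints are tested.**

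| Endpoint | Protocol 8.3.4.2 | SAP |
|---|---|---|
| Number of PRBC transfusions, Week 5 to 24 | "The number of PRBC transfusions from Week 5 to Week 24 in each treatment group will be compared using a negative binomial regression model"; no stratum or covariate named | 7.3.1: "compared using a stratified Wilcoxon rank-sum test-p-value will be calculated" |
| PRBC units, Week 5 to 24 | "in each treatment group will be compared using a Wilcoxon rank-sum test"; no stratum named | 7.3.4: "compared using a stratified Wilcoxon rank-sum test (i.e., the Van Elteren test" |

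SAP 11.1 gives the SAP precedence over the protocol. Neither SAP 7.3.1 nor 7.3.4 names its stratum, but ≥ 1/0 is the only stratification factor the SAP defines. No efficacy analysis in either document uses the count itself.

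**How the other Part A endpoints are handled.** SAP 7.2.2, 7.2.4, 7.3.2 and 7.3.5 fit MMRMs that contain the stratum and the baseline value of the same variable. This covers Hb, FACT-An, LDH, haptoglobin, indirect bilirubin, ARC, D-dimer, FACIT-F, SF-12 and EQ-5D-5L.

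**Status.** Both endpoints are ordinary secondary endpoints outside the fixed sequence (SAP 7.2), and no power is stated for them. SAP 1.1 keeps the Part A secondary analyses after enrollment was stopped short of the planned number.

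**The concern.** Within the ≥ 1 stratum, the planned test treats a patient with 1 prior transfusion and a patient with 10 as exchangeable. If past transfusion need predicts on-study need, those between-patient differences stay in the error term although a pre-randomization measure of them is already in the database. The plan removes this kind of variation for its MMRM endpoints and leaves it in here.

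What is at stake is the sensitivity of the analysis closest to the wording of a key secondary objective: "To demonstrate the effect of pegcetacoplan on the number of packed red blood cell (PRBC) transfusions in patients with CAD". The trial was planned for 57 patients and will have fewer. Validity is not at stake, because the planned rank test controls type I error.

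**Working it through.** **1. The plan's own figure.** The only stated power is for the primary endpoint (Protocol 8.1, SAP 2.3): 55 % versus 10 %, two-sided Fisher's exact test, 5 % level, 2:1 allocation. Exact enumeration gives power 0.898 at 34 + 17 and 0.925 at 36 + 18. So 54 evaluable patients reproduces, and 54/0.95 = 56.8 rounds up to 57. No such figure exists for transfusion counts, so the rest is simulation on assumed inputs.

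**2. Assumed inputs (none stand in the documents).** Each patient's rate is gamma distributed with mean μ per 6 months and shape k. The prior count is Poisson over 26 weeks. The on-study count is Poisson over 20 weeks, multiplied on drug by a rate ratio RR. Allocation is 2:1 within ≥ 1/0.

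**3. Tests compared.** The planned test sums, over strata h, w_h × (rank sum on drug − n_1h × mean rank), with w_h = 1/(n_h + 1). The adjusted test first replaces each rank r by its residual r − b(q − q̄). Here q is the rank of the prior count and b is the within-stratum least-squares slope. In the 0 stratum q is constant, so nothing changes there.

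**4. Power at N = 57, patient rates stable (1,500 trials per cell), planned → adjusted.**

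| μ, k | RR 0.5 | RR 0.35 | RR 0.2 |
|---|---|---|---|
| 1, 0.5 | 0.247 → 0.239 (-0.8) | 0.437 → 0.431 (-0.6) | 0.735 → 0.735 (0) |
| 2, 0.5 | 0.302 → 0.331 (+2.9) | 0.552 → 0.599 (+4.7) | 0.832 → 0.841 (+0.9) |
| 2, 1 | 0.406 → 0.416 (+1.0) | 0.687 → 0.722 (+3.5) | 0.921 → 0.933 (+1.2) |
| 4, 1 | 0.490 → 0.642 (+15.2) | 0.807 → 0.899 (+9.2) | 0.967 → 0.987 (+2.0) |

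The Monte Carlo standard error of one power estimate is at most √(0.25/1500) = 1.3 points. Changes of about one point either way should therefore be read as nil. Under RR = 1 the adjusted test rejected in 4.5 to 5.3 % of trials at N = 57.

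**5. What weakens the gain.**
- If only half the patients keep their rate, the same grid gives -1.3 points (0.401 → 0.388) to +2.4 points (0.441 → 0.465).
- At an assumed N of 24 with stable rates, it gives -2.9 points (0.368 → 0.339) to +7.2 points (0.229 → 0.301).

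**6. Wider scenarios.** Extending the assumptions to a higher burden (mean about 6 per 6 months) stretches the range to about -1 to +25 points at N = 57 and about -4 to +16 points at N = 24. Type I error of the adjusted test was 3.4 to 5.4 %. The upper ends come from the high-burden, moderate-effect corner. They are not ceilings, since they move with the burden assumed.

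**7. Anchor to the one relevant figure in the documents.** Protocol 4.1.2.1 reports 77 % transfusion avoidance over 12 months in the phase 2 CAD cohort. In this model, 12-month avoidance on drug is (k/(k + m))^k with m = 2 × μ × RR.
- μ = 2, k = 0.6, RR = 0.35: m = 1.4, and (0.6/2.0)^0.6 = 0.49.
- μ = 6, k = 1, RR = 0.5: m = 6, and 1/7 = 0.14.

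Both are well below 0.77. Matching 0.77 with μ = 2 and k = 1 needs m = 1/0.77 − 1 = 0.299, so RR = 0.299/4 = 0.075. With RR fitted this way (means 1, 2, 4 and 6), the change was -0.1 to +0.9 points at N = 57 and -2.8 to +1.3 at N = 24.

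**8. Negative binomial alternative (400 trials per cell, N = 57).** Adding log(count + 1) to a model with the stratum raised power at RR 0.5 from 0.410 to 0.545, from 0.475 to 0.572 and from 0.630 to 0.830. Rejection under the null was 0.088, 0.058 and 0.078 in the same three settings, so part of that gain is not real.

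**The case against.** The strongest case against is that nothing is broken. The planned test matches the randomization stratum, is simple and holds its level. Neither endpoint is in the hierarchy, and the transfusion endpoint that is key secondary is avoidance (yes/no), not the number. That stands, and it limits the point to an improvement.

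Second, the prior count may predict poorly. On-study transfusion follows the Hb thresholds in Protocol 6.1.2, and no such rule is stated for transfusions before entry. Prior therapies are washed out and then prohibited. This also stands, and it is why the half-carry-over scenarios matter.

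Third, the phase 2 figure points toward a strong effect, where the planned test already has high power at N = 57 and adjustment adds almost nothing. This stands with a caveat: that cohort was 13 open-label patients on daily dosing.

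Fourth, the documents describe a prior transfusion count, not prior units. For PRBC units the covariate is a weaker proxy, and no simulation of units was run.

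A reader might infer that adjustment is a free gain, for example of 2 to 10 points. Such figures arise when only moderate effects (RR 0.35 to 0.5), means of 2 to 6 prior transfusions and the planned 57 patients are considered (0.42 → 0.44 up to 0.38 → 0.48). The documents support neither that restriction nor the word free: they give no transfusion rates, enrollment stopped early, and small losses are possible.

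What the objections do not remove is that a pre-randomization baseline analogue is collected and left unused, while the plan's MMRM endpoints use theirs.

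**Conclusion.** The point holds as a cheap improvement to SAP 7.3.1 and, more weakly, to 7.3.4. The facts rest on the documents; the size rests on assumptions. At N = 57 the change in power is about -1 to +25 points. It is large only when prior burden is high, patient rates are stable and the drug effect is moderate. It is near nil with low burden, unstable rates or an effect as strong as the phase 2 avoidance rate. At an assumed N of 24 it is about -4 to +16 points; the final N is not given.

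The downside is a possible small loss of power if few patients are enrolled or the count predicts poorly.

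A reader might also infer from the wording of the key secondary objective that a confirmatory claim is weakened. The documents do not support that: the primary conclusion, the sample size and the fixed-sequence tests do not depend on these two analyses.

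**What to change.** Before Part A is unblinded:

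- **SAP 7.3.1.** Name ≥ 1/0 prior transfusions as the stratum. Specify a stratified rank ANCOVA: within the ≥ 1 stratum, where the count varies, regress the ranks of the on-study count on the ranks of the 6-month prior count. Then apply the Van Elteren-weighted test to the residuals, with the 0 stratum entering unadjusted. Keep the unadjusted stratified Wilcoxon test as a secondary display.
- **SAP 7.3.4.** Name the stratum here too. The same adjustment is optional, with a note that the covariate is a count of transfusions and not of units.
- **Negative binomial model.** Do not add a version adjusted for the prior count unless its type I error is first checked by simulation at the enrolled sample size.

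The cost is a sentence or two in each section and a few lines of code. No new data are needed and the sample size does not change. The price to accept knowingly is the small possible power loss described above.

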2.1 List of abbreviations and definitions

Term	Definition
Ab	Antibodies
ACIP	Advisory Committee on Immunization Practices
ADA	Antidrug antibodies
AE	Adverse event
AIHA	Autoimmune hemolytic anemia
ALT	Alanine aminotransferase
aPTT	Activated partial thromboplastin time
ARC	Absolute reticulocyte counts
AST	Aspartate aminotransferase
AxMP	Auxiliary medicinal product
B-HCG	Beta human chorionic gonadotropin
BUN	Blood urea nitrogen
C3	Complement component 3
CAD	Cold agglutinin disease
CDASH	Clinical data acquisition standards harmonization
CDISC	Clinical data interchange standards consortium
CI	Confidence interval
CMH	Cochran-Mantel-Haenszel
COVID-19	Coronavirus disease 2019
CP	Classical pathway of complement
CRO	Contract research organization
CSR	Clinical study report
CTCAE	Common Terminology Criteria for Adverse Events
DAT	Direct antiglobulin test

DNA	Deoxyribonucleic acid
EBV	Epstein-Barr virus
ECG	Electrocardiogram
eCRF	Electronic case report form
EDC	Electronic data capture
EOS	End of study
EOT	End of treatment
EQ-5D-5L	EuroQol-5 Dimension-5 Level
FACIT-F	Functional Assessment of Chronic Illness Therapy—Fatigue
FACT-An	Functional Assessment of Cancer Therapy—Anemia/Fatigue
FSH	Follicle-stimulating hormone
GCP	Good clinical practice
GGT	Gamma-glutamyltransferase
Hb	Hemoglobin
HBV	Hepatitis B virus
HCV	Hepatitis C virus
HIV	Human immunodeficiency virus
IB	Investigator's brochure
ICE	Intercurrent events
ICF	Informed consent form
ICH	International Council for Harmonisation
IEC	Independent ethics committee
IFN γ	Interferon-gamma
IgA, IgG, IgM	Immunoglobulin A, immunoglobulin G, immunoglobulin M
IL-1 β , IL-6, IL-10	Interleukin 1-beta, interleukin 6, interleukin 10
IMP	Investigational medicinal product
INR	International normalized ratio
IRB	Institutional review board
IRT	Interactive response technology

ITT	Intent-to-treat
LC-MS/MS	Liquid chromatography tandem mass spectrometry
LDH	Lactate dehydrogenase
LLN	Lower limit of normal
MedDRA	Medical Dictionary for Regulatory Activities
MI	Multiple imputation
mITT	Modified intent-to-treat
MMRM	Mixed-model for repeated measures
PCV13	Pneumococcal conjugate vaccine 13
PD	Pharmacodynamic
PEG	Polyethylene glycol
PK	Pharmacokinetic(s)
PNH	Paroxysmal nocturnal hemoglobinuria
PP	Per-protocol
PPSV23	Pneumococcal polysaccharide vaccine 23
PRBCs	Packed red blood cells
PT	Preferred term
RBC	Red blood cell
SAE	Serious adverse event
SAP	Statistical analysis plan
s.c.	Subcutaneous
SOC	System organ class
SF-12	12-Item Short Form Survey
SUSAR	Suspected Unexpected Serious Adverse Reaction
TEAE	Treatment-emergent adverse event
TNF α	Tumor necrosis factor-alpha
ULN	Upper limit of normal
US	United States
WHO	World Health Organization

WOCBP

Women of childbearing potential

3 **Ethics**

3.1 Independent ethics committee and/or institutional review board

It is the responsibility of the investigator to obtain approval of the study protocol, possible amendments and the written patient information and ICF from the IEC/IRB. The investigator should file all correspondence with the IEC/IRB. Copies of IEC/IRB correspondence and approvals should be forwarded to Swedish Orphan Biovitrum (Sobi).

3.2 Ethical conduct of the study

This study will be conducted in compliance with this protocol, the ICH GCP [1], applicable regulatory requirements, and in accordance with the ethical principles that have their origin in the Declaration of Helsinki [2].

